Previous research relied heavily on participants' perceptions to rate a drug's effectiveness and purpose; this study was designed with randomized, placebo-controlled trials to evaluate the main goal using objective quantitative data. I will use neuropsychological testing to assess if tablet size affects participants' short-term memory, executive function, and processing speed using caffeine as the drug of choice. Previous research has supported a significant cognitive boost in these cognitive functions for caffeine dosages of at least 75 mg (EFSA, 2011). If tablet size affects perceptions of how effective a dose of caffeine will be, despite doses remaining constant in the caffeinated groups, then I expect significant differences among the two tablet sizes for processing speed, executive functioning, and memory capabilities in participants. This study may prove foundational to better understanding more effective physical drug designs.

Hypotheses

There are three hypotheses for this experiment:

- caffeine will significantly improve participant's memory, executive function, and processing speed;
- there will be a significant difference in participant performance associated with tablet size;
- 3) there will be an interaction effect between caffeine content and tablet size.

Method

Participants

120 participants, primarily Psychology students fulfilling a research participation requirement for Introduction to Psychology courses, will be recruited. Ambulatory participants that are fluent in written and spoken English will be used because they should be able to complete the neuropsychological tests.

Participants that are allergic to sucrose and/or caffeine will be excluded because they are essential components to the procedure. Participants with cardiovascular disease or uncontrolled high blood pressure will be excluded because the use of caffeine may exacerbate these conditions. Participants with untreated or unresolved anxiety and/or depressive disorders will be excluded because caffeine may exacerbate symptoms related to these disorders as well. Participants that are pregnant will be excluded from this study. Lastly, participants that have a diagnosed learning disability will be excluded because the neuropsychological tests will only use scores normalized for the general population.

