Participants' age will be limited to ages 18 years old through 40 years old because age is a significant factor in caffeine metabolism (Kinirons & O'Mahony, 2004). Individuals older than 40 may experience different pharmacological effects due to age; thus, age will be controlled in this study.

Measures

Processing Speed.

Stroop 1) Color and 2) Word tests.

The Color test asks participants to read the color of print on a page with columns of red, yellow, green, and blue X s. The Word test asks participants to read the printed words on a page with the words RED, YELLOW, GREEN, and BLUE printed in black ink. These tests are scored by timing, in seconds, how long participants take to correctly identify the 100 items in each test. Longer completion times indicate slower processing speed capabilities. The Stroop Test's separate 1) Color and 2) Word tests (Appendix B) test-retest reliabilities are .83 and .74, respectively (Franzen, et al., 1987)

Trail Making Task A.

This test asks participants to connect a series of numbers that are randomly distributed on the test page. The goal of these tasks is to connect the series of numbers or numbers and letters in order (e.g. 1-2-3) as quickly as possible. Scoring is done by recording the time (in seconds) participants needed to complete the test. Longer completion times indicate slower processing speed capabilities. The Chronbach's alpha reliability of Trail A is .86 (Smith, et al., 2008).

Executive Function.

Stroop 3) Color-and-Word test.

The Color-and-Word test asks participants to read the color of print for the words RED, YELLOW, GREEN, and BLUE when the print color and word conflict. This test is scored by timing, in seconds, how long it takes for participants to correctly read 100 items. Longer completion times indicate lower executive function capabilities because the conflict between the print color and printed word takes longer to overcome. The test-retest reliability of the Stroop Colorand-Word Test is .67 (Franzen, et al., 1987).

Trail Making Task B.

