Primary analysis will be done through a series of ANCOVAs, if a preliminary correlation analysis shows a significant relationship between weekly caffeine consumption and scoring for each cognitive component. If the preliminary correlation analysis does not show a significant relationship between weekly caffeine consumption and scores for each cognitive component, then a series of ANOVAs will be performed.

Proposed Timeline

Pending the approval of clinicaltrials.gov, materials will be gathered and prepared in early October. The UROP has been awarded and funds will be available once PRS has approved of this proposal. Recruitment will begin during the Fall semester. Recruitment and trials are expected to continue in through December and conclude as late as February. Course load will be kept to a minimum to allot enough time for trials every weekday during the morning.

[figure not shown]
15

Weekly caffeine consumption will be calculated for each participant from their reported

caffeine consumption habits (Appendix E).

	No caffeine	90 mg caffeine
Small tablet (1 mm diameter)	Average score on cogitive test	Average score on cognitive test
Large tablet (5 mm diameter)	Average score on cognitive test	Average score on cognitive test

Figure 1. Overall study design

The Effect of Tablet Size on Cognitive Performance: A RCT Using Caffeine

Figure 2. CONSORT diagram

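### The primary series of tests has no stated alpha, component score, success rule or multiplicity control, so the false-positive chance for tablet size depends on a rule not yet chosen

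*Combined protocol and SAP*

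**What the plan says.** The analysis plan is the short Data Analysis section. It opens "Primary analysis will be done through a series of ANCOVAs", on condition that a preliminary correlation between weekly caffeine intake and the scores is significant. Otherwise the wording is "scores for each cognitive component, then a series of ANOVAs will be performed". The unit of analysis is therefore the cognitive component.

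Present Study names three components: "short-term memory, executive function, and processing speed using caffeine as the drug of choice". For tablet size it adds: "I expect significant differences among the two tablet sizes for processing speed, executive functioning, and memory capabilities in participants". Under Hypotheses, the caffeine hypothesis also lists all three: "caffeine will significantly improve participant's memory, executive function, and processing speed". The tablet-size hypothesis lists none: "there will be a significant difference in participant performance associated with tablet size". The third hypothesis is an interaction.

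Measures defines scores for single tests only:
- Processing speed: Stroop Color time, Stroop Word time, Trail A time.
- Executive function: Stroop Color-and-Word time, Trail B time.
- Memory: RAVLT words recalled, % recalled (A7 divided by A5) and intrusions. The text reads a higher percentage with few intrusions as better memory.

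That makes eight scores, with no rule for combining them. Each cell of Figure 1 holds a mean for a cognitive test, not for a component. Procedure gives 120 participants at 0.80 power, without an effect size, SD or alpha.

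**The concern.** Tablet size is the trial's main question, and the tablet-size hypothesis can be declared supported in several ways. The investigator could require significance on all three components, accept any one component, or accept any single test score. The wording of Present Study leans towards the first. The claim in Procedure that 120 participants suffice to detect any significant effect leans towards the second or third, and Figure 1 permits the third. Nothing in the plan chooses between them.

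Each single test keeps its own error rate. What is not controlled is the claim built on several tests. If the rule is settled after results are known, a reader cannot tell whether a positive report met a strict standard or a loose one, and no later analysis can repair that credibly.

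**Working it through.** **The plan's own figure.** The only design figure is N = 120 at 80% power. It can be neither reproduced nor refuted, because no effect size, SD, alpha or sidedness is given. Solving backwards for 60 v 60 at two-sided 0.05: (1.960 + 0.842) × √(2/60) = 0.51 SD. With the noncentral t on 115 df (120 − 4 cells − 1 covariate) it is 0.516 SD. That value is an assumption below, not a figure from the plan.

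**Inputs.** Three components (Present Study); eight scores (counted from Measures); 60 per tablet size (120 over four groups, assumed equal). Assumed because not stated: alpha 0.05; two-sided, since the tablet-size hypothesis has no direction; equal correlation ρ between test statistics, from 0 to 0.7, with 0.9 as a sensitivity value; no true tablet-size effect.

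**Formula.** For k equicorrelated normal statistics with cut-off c = 1.96, let p(u) = Φ[(c − √ρ·u)/√(1−ρ)] − Φ[(−c − √ρ·u)/√(1−ρ)]. Then, integrating over the standard normal density φ(u):
- P(any) = 1 − ∫ φ(u)·p(u)^k du
- P(all) = ∫ φ(u)·[1 − p(u)]^k du

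At ρ = 0 and k = 3 these reduce to 1 − 0.95³ = 14.3% and 0.05³ = 0.0125%. At k = 8, 1 − 0.95⁸ = 33.7%.

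| Rule for claiming a tablet-size effect | ρ = 0 | 0.3 | 0.5 | 0.7 | 0.9 |
|---|---|---|---|---|---|
| All three components | 0.01% | 0.09% | 0.32% | 0.89% | 2.3% |
| Any one of three components | 14.3% | 13.6% | 12.5% | 10.9% | 8.4% |
| Any one of eight scores | 33.7% | 30.0% | 25.0% | 19.1% | 11.9% |
| Any one of three, first Holm step (0.05/3 = 0.0167) | 4.9% | 4.8% | 4.5% | 3.9% | 3.0% |

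Simulated 2×2 trials with 30 per cell agree: at ρ = 0, 0.3, 0.5 and 0.7, any-of-three was 14.2%, 13.5%, 12.6% and 10.9%, and all-three 0.01%, 0.08%, 0.30% and 0.85% (100,000 runs each).

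**Power cost of Holm** (noncentral t, 60 v 60, 115 df, strictest step 0.0167 against 0.05):
- Main effect detectable with 80% power: 0.52 SD rises to 0.60 SD.
- Power at 0.516 SD: 80% falls to 65%.
- Power at an assumed tablet effect of 0.3 SD: 37% falls to 22%.

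**The case against.** The best defence is that the components are joined by "and" in the expectation for tablet size and in the caffeine hypothesis. If that is an all-three rule, the error is already far below 5% and no adjustment is needed. This is right as far as it goes, but the sentences state expectations, not decision rules, and the tablet-size hypothesis itself names no component. If the all-three rule is intended, one sentence would settle it.

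It is also fair that the correlation range is assumed. Speed and executive function share the Stroop and Trail families, so those two could correlate strongly. At 0.9 the any-one figure drops to 8.4% and the all-three figure rises to 2.3%. The first is still above 5%, and the gap between rules remains almost fourfold. Similarly, the 34% end of the eight-score range needs uncorrelated scores, which is unlikely when three come from one Stroop test.

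Three stronger readings are tempting but not supported:
- A reader might infer that the plan contradicts itself because Participants says "the neuropsychological tests will only use scores normalized for the general population" while Measures says "These tests are scored by timing, in seconds, how long participants take to correctly identify the 100 items in each test". Norms are applied to raw times, and the first sentence explains an exclusion criterion. At most, a conversion step is unstated.
- A reader might count further lines on the Appendix B and D scoring sheets, such as Stroop errors, as extra outcomes. These are stock forms (the RAVLT sheet carries another study's title) and do not show planned analyses.
- A reader might conclude that Holm is indispensable. It is needed only if any one component can carry a hypothesis.

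**Conclusion.** The omission is real and should be corrected before any data are seen. The document supports no single error rate for the trial: it would be wrong to say that the plan has an 11% to 14% or a 34% false-positive rate. The supported statement is that the rate for tablet size runs from 0.01%–0.9% (all three components) through 11%–14% (any one component) to 19%–34% (any one score), depending on a rule the plan leaves open. These ranges rest on two-sided alpha 0.05, no true tablet-size effect and equal correlations of 0 to 0.7, none of which the document states. The direction of the finding does not depend on the exact correlation.

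The choice between ANCOVA and ANOVA by a preliminary correlation test is a separate matter and is not part of these figures.

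**What to change.** Before data are seen, add to Data Analysis:

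1. **Alpha and scores.** Two-sided alpha 0.05 and one primary score per component. Speed: average of Stroop Color, Stroop Word and Trail A. Executive function: average of Stroop Color-and-Word and Trail B. Put the tests on a common standardized scale first, signed so that higher is better. Memory: one RAVLT score, either % recalled (the measure that Measures interprets) or the A1–A5 total. Do not average these two, because a gain in A5 raises the total and lowers the ratio. For example, with A7 = 10, moving A5 from 12 to 13 adds a word to the total but takes A7/A5 from 83.3% to 76.9%.
2. **Success rule.** If any one component can support a hypothesis, apply Holm over the three components within that hypothesis and claim only the components that survive. If all three must be significant, say so; no adjustment is then needed.
3. **Scope.** State that error is held at 5% within each hypothesis, not across the three (if independent, 1 − 0.95³ = 14.3% over all three). Report single-score tests as descriptive, with confidence intervals.
4. **Separately, at no cost.** Include weekly caffeine intake as a covariate in every model instead of choosing the model by a preliminary correlation test.

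No new data are needed, but either success rule costs power. Under Holm, the loss at the strictest step is as shown in the working. In simulation with a caffeine effect of 0.516 SD on all three components, Holm power is about 72% to 74% per component. Under an unadjusted all-three rule, the chance of success is 50% to 65%. The power statement in Procedure should be restated for a named outcome, effect size and alpha, so that this loss is accepted knowingly.

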Caffeine may be a good option for testing this phenomenon for three reasons: 1) previous research already supports caffeine's improvements to cognitive functioning (EFSA, 2011); 2) caffeine use among college students is very salient, given the prominence of the caffeine across various products like energy drinks (Pettit & DeBarr, 2011); 3) using self-report measures to collect data on weekly caffeine consumption habits will allow adjustments for tolerance effects (Beaumont, et al., 2017;2016). Research on caffeine use in healthy adults has already shown significant improvement to memory, executive functioning, and processing speed (EFSA, 2011). Caffeine lends itself well to a randomized controlled trial design, allowing the introduction of tablet size as an additional factor. Previous research supports an increase in cognitive functioning after consuming caffeine; memory, executive functioning, and processing speed are improved after consuming caffeine (EFSA, 2011). The European Food and Safety Administration conducted a meta-analysis that assessed the different claims associated with consuming caffeine like increased fat oxidation, increased energy expenditure, increased

alertness, and increased attention. Their findings suggest that there is not enough data to support causal claims for caffeine causing increased fat oxidation and increased energy expenditure. However, a causal relationship between caffeine and increased alertness and increased attention is supported (EFSA, 2011). Pettit and Debarr conducted a study analyzing the association between stress and energy drink consumption, and the association between energy drink consumption and GPA in 136 college students ages 18-24 (Pettit & DeBarr, 2011). Their results show a positive correlation between perceived stress and energy drink consumption, and a negative correlation between GPA and energy drink consumption. However, the results in Pettit and DeBarr's study did not account for consumption of caffeine from other sources (e.g. coffee, tea, supplements, etc.). Heavy marketing for caffeinated products make caffeine an ideal substance to use for assessments when working with college students.

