Beaumont et al.'s research on tolerance development for low doses of caffeine emphasizes the need to adjust for tolerance effects in randomized controlled trials (Beaumont, et al., 2016; 2017;). Their research examined participant physical performance after consuming small doses of caffeine. Participants experienced significant decline in performance after consuming small doses of caffeine (1.5 mg of caffeine per kg of bodyweight) for 28 consecutive days compared to placebo. Beaumont et al.'s work highlights the importance of adjusting for participants' caffeine consumption habits. Leaving scores unadjusted for caffeine consumption habits could be a confound to studies that involve participants consuming caffeine.

Lastly, age is a significant factor in caffeine metabolism. Some hepatic enzymes (Cytochrome P450s, or CYPs) become less active as individuals age (Kinirons & O'Mahony,

8

2004). There are several different CYPs that metabolize different drugs. Caffeine is metabolized by CYPs in the 1A family, specifically 1A2 CYPs. Kinirons and O'Mahony's literature analysis showed consistent decrease in enzyme activity as individuals age (Kinirons & O'Mahony, 2004). They suggest the decreases in certain enzyme activity are likely due to changes in liver size and blood flow. Livers in humans experience a size reduction and reduced blood flow with age. When conducting research that involves participants metabolizing caffeine, age should be considered. Caffeine is a good choice to examine the effects tablet size may have on participants' performances on cognitive tests.

Present Study

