This test asks participants to connect a series of numbers and letters that are randomly distributed on the test page. The goal of these tasks is to connect the series of numbers and letters in order (e.g. 1-A-2-B-3-C) as quickly as possible (Appendix C). Switching between alphabetic and numeric sets and timing completion times, in seconds, is an effective measure of executive functioning capabilities. Longer completion times indicate lower executive function capabilities because participants take longer to switch between sets. The Cronbach's alpha of Trail B is .88 (Smith, et al., 2008).

Memory.

Rey Auditory Verbal Learning Test (RAVLT).

Participants are presented with 15 unrelated words and asked to recall as many as they can over five trials. This section assesses immediate recall ability. An additional 15 unrelated words are then introduced as an interference component. Participants must recall as many of the original 15 words as possible after being presented with interference. Lastly, after an interval of 30 minutes, participants are asked to recall the original 15 words again (Appendix D). The trials are scored by counting the correct number of words recalled, the % recalled (the final delayed-recall trial(A7) divided by the final immediate recall trial (A5)), and the number of intrusions (i.e. the number of incorrect words). A higher percentage of recall with little to no intrusions are considered better memory. The Cronbach's alpha reliability of the Rey Auditory Verbal learning Test is .84 (Magalhaes, et al., 2012).

Procedure

Materials for this procedure will need to be prepared beforehand. 90 mg packets of caffeine will be prepared from 200 mg pure caffeine powder capsules by opening capsules and measuring out the desired weight of caffeine using a scale that can measure accurately to the thousandths gram. The weight of each prepared packet will be recorded by hand in a notebook until it is used in a trial. Before participants arrive, the prepared caffeine packet will be mixed with distilled water and one pillule of each size will be placed into small paper cups marked A and B.

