Procedures will be explained to participants at first contact, and they will sign an informed consent form to confirm eligibility (Figure 2). Participants will be randomly assigned to one of the four groups (Figure 1). Based on a power analysis conducted at 0.80 power on Pasman et al.'s work on the effects of caffeine in a home-setting, 120 participants will need to be recruited in this study to successfully detect any significant effect (Pasman et al., 2017).

Participants will be required to not have consumed caffeine the day of testing. Participants will be presented with 8 ounces of distilled water and the cups containing each sucrose placebo pill. They will be asked to drink the water and only one of the sucrose pillules (depending on the group they were placed in); half of the participants (n=60) will drink water mixed with 90 mg of dissolved caffeine (Figure 1). After consumption, participants will be asked to complete Velten's Neutral Mood Induction Procedure (Appendix A) until 30 minutes have passed to allow for caffeine activation in the body (Institute of Medicine (US) Committee on Military Nutrition Research, 2001). Participants will then begin with the series of Stroop tests. After completing the three Stroop tests, participants will complete the first section of the Rey Auditory Verbal Learning test (immediate recall). During the 30-minute waiting period

participants will complete Trail Making Tasks A and B, and fill out a demographic survey designed to collect: 1) their weekly caffeine intake using the Caffeine Consumption Questionnaire (Appendix E); 2) sex; 3) age; 4) ethnicity and race; 5) year in school (i.e. freshman, sophomore, etc.); 6) GPA; and 7) academic major. The time of day the trial begins will also be recorded. The data collected in the survey will be used to adjust scores during data analyses. If students are unable to complete the survey and caffeine questionnaire within the 30-minute waiting period allotted for the RAVLT, the survey materials will be set aside and completed after participants finish the second component of the RAVLT. After completing the second portion of the RAVLT participants will be debriefed, and the trial will conclude.

Data Analysis

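### Whether the primary model adjusts for weekly caffeine intake is decided by a significance test on the outcome data, which does not match the unconditional adjustment stated under Procedure

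*Combined protocol and SAP*

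**What the plan says.** Data Analysis makes the primary analysis conditional. ANCOVAs are used "if a preliminary correlation analysis shows a significant relationship between weekly caffeine consumption and scoring for each cognitive component". If the correlation "does not show a significant relationship between weekly caffeine consumption and scores for each cognitive component, then a series of ANOVAs will be performed". No significance level, sidedness or type of correlation is given for this screen.

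Procedure lists seven survey items, with weekly caffeine intake first, and then states: "The data collected in the survey will be used to adjust scores during data analyses". No condition is attached. The sentence also covers items such as sex, age and GPA, which Data Analysis never names as covariates.

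The Caffeine section of the introduction gives the reason for collecting intake: "using self-report measures to collect data on weekly caffeine consumption habits will allow adjustments for tolerance effects". It says that the cited tolerance research "emphasizes the need to adjust for tolerance effects in randomized controlled trials", and adds: "Leaving scores unadjusted for caffeine consumption habits could be a confound".

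A cognitive component is not tied to one score. The hypotheses name three domains. Measures lists eight scores: Stroop Color, Stroop Word and Trail Making A for processing speed; Stroop Color-and-Word and Trail Making B for executive function; and three for memory, where "The trials are scored by counting the correct number of words recalled, the % recalled" and the number of intrusions. No composite is defined.

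**The concern.** The adjustment set of a primary model should be known before outcomes are examined. Here the outcomes decide it. The rule is written in advance and does not look at the caffeine or tablet-size contrasts, but it still leaves three matters open.

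- **Which model is primary.** It depends on whether a sample correlation crosses a threshold.
- **Whether the adjustment stated under Procedure is made at all.** A non-significant screen does not show that intake is unrelated to the score.
- **How the rule is applied.** Read component by component, different outcomes can get different models. Read jointly, a mixed result either falls to ANOVA or is not clearly covered.

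Two careful analysts could fit different primary models to the same data, each able to point to the text in support.

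**Working it through.** **Inputs.** From the documents: n = 120, 60 with and 60 without caffeine, four groups (30 per cell if equal), 0.80 power, three cognitive domains. Not in the documents and therefore assumed: two-sided alpha of 0.05 for the screen and the main tests, the true intake-score correlation r, equal r across components, residual correlation of 0.3-0.7 between components, and the effect size.

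**The plan's own figure.** The 120 cannot be reproduced, because no effect size, SD, alpha or test is given. Solving backwards for 60 against 60: d = (1.96 + 0.84) × √(2/60) = 0.51. The simulations use 0.515 or 0.516 SD, which gives about 80% power for the caffeine effect in the unadjusted model. Nothing below is a claim about whether 120 is right.

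**Screen threshold.** Critical |r| = t/√(n − 2 + t²), with t = 1.980 on 118 df: 1.980/√(118 + 3.92) = 0.179, or 3.2% of variance.

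**Chance of passing, one component.** By Fisher's z at r = 0.20: atanh(0.20) × √117 = 2.19, and Φ(2.19 − 1.96) = 0.59. Adjustment is dropped in about 41% of trials.

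**Joint decision.** Simulated probabilities that all three components are significant at r = 0.20 are 0.295, 0.352 and 0.410 for residual correlations 0.3, 0.5 and 0.7. The drop rates are therefore 1 − 0.295 = 71%, 65% and 59%.

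| True r | Dropped, per component | Dropped, joint |
|---|---|---|
| 0.10 | 81% | 93-98% |
| 0.15 | 63% | 80-89% |
| 0.20 | 41% | 59-71% |
| 0.25 | 21% | 35-44% |
| 0.30 | 8% | 15-20% |
| 0.40 | 0.4% | 1% |

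A second simulation of the joint rule at r = 0.20 gave 61-72%, so about 60-72% is a fair summary. A caffeine effect in the data weakens the raw correlation a little: with 0.515 SD the per-component pass rate at r = 0.20 is 0.569, so 43% are dropped.

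**Error and power, per-component rule** (200,000 simulated 2×2 trials per setting, 30 per cell, caffeine main effect):

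| True r | Type I error, screened rule | Power: ANOVA | Power: screened rule | Power: always ANCOVA |
|---|---|---|---|---|
| 0 | 0.049 | 0.800 | 0.799 | 0.797 |
| 0.1 | 0.051 | 0.798 | 0.798 | 0.799 |
| 0.2 | 0.049 | 0.798 | 0.805 | 0.811 |
| 0.3 | 0.051 | 0.798 | 0.828 | 0.831 |
| 0.4 | 0.049 | 0.801 | 0.859 | 0.860 |

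The largest loss in the table is 0.811 − 0.805 = 0.6 points (0.5 before rounding). Under the joint rule the loss reaches about 1.4 points, because adjustment is dropped more often. Type I error stays near 5% there too. At r = 0 the screen costs nothing.

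**The case against.** The strongest reply is that almost nothing turns on this numerically. The rule is mechanical, blind to the treatment contrasts, and holds its error rate. When the screen fails, the two models disagree on significance in only 2.0-3.4% of those trials at r = 0.10-0.30. That stands, and it limits the point to pre-specification and consistency.

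A second reply is that the Procedure sentence only explains why the survey is collected, and that Data Analysis supplies the specific rule. The introduction's language on adjustment is also partly permissive. This reading is possible, but no text says that one section governs the other, and the two differ in scope as well as in condition.

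A third is that a per-component decision is the more natural reading, since a series of models is planned. That is fair, and the 60-72% applies only to the joint reading. The wording permits both.

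Three stronger inferences are tempting and should not be drawn.

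- **That the screen inflates type I error.** A rate of about 5.5-7% arises only if both models are run and whichever is significant is reported. Data Analysis does not permit that.
- **That an unadjusted analysis is confounded.** The introduction uses that word, but allocation is random, so the unadjusted comparison is unbiased on average.
- **That adding intake to the model deals with tolerance.** Tolerance would change the caffeine effect itself. A common intake slope does not represent that; an intake × caffeine term would be needed.

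**Conclusion.** The point holds and should be corrected. The plan leaves the primary model to a test on its own outcomes, states the adjustment differently in two sections, and words the rule so that it can be applied in two ways.

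At an assumed r of 0.20 the choice of reading alone moves the chance of dropping adjustment from about 41% to about 60-72%. The inferential cost is small: type I error near 5% under either reading, and a power loss of at most about 0.6 points per component or about 1.4 points jointly. These figures rest on the assumed alpha, effect size, equal r and between-component correlation. The textual findings do not.

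**What to change.** Delete the preliminary correlation step and replace it under Data Analysis with:

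*Each outcome score will be analysed with one ANCOVA containing caffeine, tablet size, caffeine × tablet size and weekly caffeine intake, whatever the observed correlation. This is the primary model; the unadjusted 2×2 ANOVA is a sensitivity analysis and does not replace it.*

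Under Procedure, replace the adjustment sentence with:

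*Weekly caffeine intake will be used to adjust scores as set out under Data Analysis.*

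Fix the calculation that turns the Appendix E entries into one weekly figure before outcomes are examined.

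**Cost.** Wording only, with no new data. Residual degrees of freedom go from 120 − 4 = 116 to 120 − 5 = 115. If intake is unrelated to a score, the covariate buys nothing and costs about 0.3 points of power against ANOVA (0.800 to 0.797).

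**One assumption to state.** Intake is self-reported after dosing, and under Procedure, if time runs out, "the survey materials will be set aside and completed after participants finish the second component of the RAVLT". The plan should say that reporting of habitual intake is assumed to be unaffected by allocation, and show the unadjusted ANOVA as the check. It should not describe the common-slope term as a model of tolerance.

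The change leaves the number of outcome scores and tests as it is; multiplicity is a separate matter.
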